5.2 Exclusion Criteria

Patients meeting any of the following exclusion criteria are not to be enrolled in the study:

1. Female patients who are lactating or have a positive serum pregnancy test during the screening period.
2. Major surgery within 14 days before enrollment.
 - Does not include placement of venous access device, bone marrow biopsy, GVHD diagnostic biopsy, or other routine procedures in chronic GVHD or post-transplantation care.
3. Uncontrolled infection within 14 days before study enrollment.

- Infection treated with appropriate antimicrobial therapy and without signs of progression/treatment failure does not constitute an exclusion criterion

4. Evidence of current uncontrolled cardiovascular conditions, including uncontrolled hypertension, uncontrolled cardiac arrhythmias, symptomatic congestive heart failure, unstable angina, or myocardial infarction within the past 6 months.

- Chronic hypertension on medical therapy does not constitute an exclusion criterion.

5. Systemic treatment, within 14 days before the first dose of Ixazomib, with strong inhibitors of CYP1A2 (fluvoxamine, enoxacin, ciprofloxacin), strong inhibitors of CYP3A (clarithromycin, telithromycin, itraconazole, voriconazole, ketoconazole, nefazodone, posaconazole) or strong CYP3A inducers (rifampin, rifapentine, rifabutin, carbamazepine, phenytoin, phenobarbital), or use of Ginkgo biloba or St. John's wort.

6. Active hepatitis B or C virus infection, or known human immunodeficiency virus (HIV) positive.

7. Any serious medical or psychiatric illness that could, in the investigator's opinion, potentially interfere with the completion of treatment according to this protocol.

8. Known allergy to any of the study medications, their analogues, or excipients in the various formulations of any agent.

9. Non-hematologic malignancy within the past 2 years with the exception of:

- adequately treated basal cell carcinoma, squamous cell skin cancer, or thyroid cancer
- carcinoma *in situ* of the cervix or breast
- prostate cancer of Gleason Grade 6 or less with stable prostate-specific antigen levels
- cancer considered cured by surgical resection or unlikely to impact survival during the duration of the study

10. Patient has \geq Grade 3 peripheral neuropathy, or Grade 2 with pain on clinical examination during the screening period.
11. Treatment with non-FDA approved drug within 21 days of start of this trial
12. New systemic immune suppressive agent added for the treatment of chronic GVHD within 2 weeks prior to enrollment
 - Addition of a new systemic immune suppressive treatment simultaneously with ixazomib is also prohibited.
13. Evidence of recurrent or progressive underlying malignant disease.
14. Karnofsky performance status < 70%
15. Life expectancy less than 6 months

6. STUDY DRUG

6.1 Study Drug Administration

Ixazomib will be administered at 4mg oral dose once weekly on days 1, 8, and 15 of a 28-day cycle. Up to 6 total cycles of therapy will be delivered on trial, and patients will be followed through 1 year of total clinical follow up for study endpoints.

Patients experiencing a CR, PR, or stable disease at 6 months will be given the option to continue on ixazomib for up to an additional 6 cycles (for a total of up to 12 cycles, or maximum 36 doses). See section 4.3 for additional details.

Sufficient study drug will be dispensed at each study visit to cover one 28 day treatment cycle. Study patients will document their compliance through medication logs.

Ixazomib Administration

All protocol-specific criteria for administration of study drug must be met and documented before drug administration. Study drug will be administered or dispensed only to eligible

patients under the supervision of the investigator or identified subinvestigator(s). Patients should be monitored for toxicity, as necessary, and doses of Ixazomib should be modified as needed to accommodate patient tolerance to treatment; this may include symptomatic treatment, dose interruptions, and adjustments of Ixazomib dose (see Section 6.2). Due to the common side effect of nausea, it is recommended (but not required) that participants take Zofran (ondansetron) 8 mg PO, 30-60 minutes prior to each dose, and 8 hours after each dose. Additional doses of Zofran may be taken as needed, up to 24 mg in a 24-hour period.

The prescribed administration of Ixazomib doses in this study is 4mg oral dose once weekly on days 1, 8, and 15 of a 28-day cycle. Patients should be instructed to swallow Ixazomib capsules whole, with water, and not to break, chew, or open the capsules. Study drug should be taken on an empty stomach. Patients should not have any food or drink (other than water) for at least 2 hours before taking drug, and for at least 1 hour after taking drug. A total of approximately 8 ounces (240 mL) of water should be taken with the capsule.

Missed doses can be taken as soon as the patient remembers if the next scheduled dose is 72 hours or more away. A double dose should not be taken to make up for a missed dose. If the patient vomits after taking a dose, the patient should not repeat the dose but should resume dosing at the time of the next scheduled dose.

Ixazomib Destruction

Investigational Ixazomib (expired or end of study) should be destroyed on site according to the institution's standard operating procedure, and removal and destruction will be documented on drug accountability logs.

6.2 Dose-Modification Guidelines

6.2.1 Recommended Ixazomib Criteria for Beginning or Delaying a Subsequent Treatment Cycle & Dose Modifications for Treatment Associated Toxicity

Treatment with Ixazomib will use a cycle length of 28 days. The next cycle should begin as soon as possible, but no later than 14 days after the end of the previous cycle. Unavoidable deviations from this schedule will be permissible with prior approval by the Principal Investigator or Study Chair. For a new cycle of treatment to begin, the patient must meet the following criteria within 3 days prior to drug being dispensed:

- ANC must be $\geq 1,000/\text{mm}^3$.

- Platelet count must be $\geq 75,000/\text{mm}^3$.
- All other non-hematologic toxicity (except for alopecia) must have resolved to \leq Grade 1 or to the patient's baseline condition

These laboratory tests should be performed and reviewed at the study site.

If the patient fails to meet the above-cited criteria for initiation of the next cycle of treatment, dosing should be delayed for 1 week. At the end of that time, the patient should be re-evaluated to determine whether the criteria have been met. If the patient continues to fail to meet the above-cited criteria, delay therapy and continue to re-evaluate. The maximum delay before treatment should be discontinued will be 3 weeks or at the discretion of the Principal Investigator.

Ixazomib dose adjustments are described in table 6-1. For dosing recommendations for hematologic toxicities and non-hematologic toxicities, see Table 6-2 and Table 6-3 respectively.

Table 6-1 Ixazomib Dose Adjustments

Dose Level	Dose (mg)
Starting Dose	4.0 mg
-1	3.0 mg
-2	2.3 mg
-3	Discontinue

Table 6-2 Ixazomib Dose Adjustments for Hematologic Toxicities

Criteria	Action
Within-Cycle Dose Modifications	

 • If platelet count $\leq 30 \times 10^9/L$ or ANC $\leq 0.50 \times 10^9/L$ on a Ixazomib dosing day (other than Day 1) 	
 • Ixazomib dose should be withheld. • Complete blood count (CBC) with differential should be repeated until the ANC and/or platelet counts have exceeded the prespecified values (see Section 6.2.1) • Upon recovery, Ixazomib may be reinitiated with 1 dose level reduction.
Dose Modifications for Subsequent Treatment Cycles	

 • ANC $< 1.0 \times 10^9/L$, platelet count $< 75 \times 10^9/L$, or other non-hematologic toxicities $>$ Grade 1 or not to the patient's baseline condition 	
 • Hold Ixazomib until resolution as per criteria Section 6.2. • Upon recovery, reduce Ixazomib 1 dose level. • The maximum delay before treatment should be discontinued will be 3 weeks or at the discretion of the PI.
Dose Modifications for Subsequent Treatment Cycles	

 • All hematologic toxicities 	
 • For hematologic toxicity that occurs during a cycle but recover in time for the start of the next cycle: 
 ◦ If dose was reduced within the cycle, start the next cycle at that same dose. ◦ If due to toxicity timing, ie, after Day 15 dosing thus a dose reduction was not required at that point in the cycle, reduce Ixazomib by 1 dose level at the start of that cycle. ◦ Do not reduce the dose both within a cycle and at the start of the cycle for the same most severe toxicity.

Table 6-3 Ixazomib Treatment Modification (Delays, Reductions, and Discontinuations) Due to Adverse Events (Non-Hematologic Toxicities)

Adverse Event (Severity)	Action on Study Drug	Further Considerations
Peripheral Neuropathy:		
Grade 1 peripheral neuropathy	
 • No action 	Grade 1 signs and symptoms: asymptomatic; without pain or loss of function; clinical or diagnostic observations only [14]
New or worsening Grade 1 peripheral neuropathy with pain or Grade 2	
 • Hold study drug until resolution to Grade ≤ 1 or baseline • Resume at same dose level 	Grade 2 signs and symptoms: Moderate symptoms; limiting instrumental activities of daily living (ADL) [14]
New or worsening Grade 2 peripheral neuropathy with pain or Grade 3	
 • Hold study drug until resolution to Grade ≤ 1 or baseline • Reduce study drug to next lower dose upon recovery 	Grade 3 signs and symptoms: severe symptoms; limiting self-care ADL; assistive device indicated [14]
New or worsening Grade 4 peripheral neuropathy	
 • Discontinue study drug 	
Grade 2 Rash	Symptomatic recommendations as per section 6.6	The investigator and project clinician may discuss considerations for dose modifications and symptom management.
Other Grade 3 non-hematologic toxicity judged to be related to study drug	
 • Hold study drug until resolution to Grade < 1 or baseline 	Symptomatic recommendations noted in Section 6.6
If recovered to $<$ Grade 1 or baseline within 4 weeks	Reduce study drug 1 to next lower dose upon return to $<$ Grade 1 or baseline	

Table 6-3 Ixazomib Treatment Modification (Delays, Reductions, and Discontinuations) Due to Adverse Events (Non-Hematologic Toxicities)

Adverse Event (Severity)	Action on Study Drug	Further Considerations
If not recovered to < Grade 1 or baseline within 4 weeks	
 Reduce study drug 1 to next lower dose upon return to < Grade 1 or baseline 	
Subsequent recurrence	
 Follow above management guidelines 	Monitor closely, take appropriate medical precautions, and provide appropriate symptomatic care
Grade 3 that does not recover to < Grade 1 or baseline within 4 weeks	
 Reduce study drug to next lower dose 	
Grade 4 nonhematologic toxicities judged to be related to study drug	Consider permanently discontinuing study drug	Exceptions are cases in which the investigator determines the patient is obtaining a clinical benefit

Once Ixazomib is reduced for any toxicity, the dose may not be re-escalated.

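### After related Grade 3 non-hematologic toxicity, section 6.2.1 and Table 6-2 stop ixazomib by default at a 3-week delay, while Table 6-3 re-doses with no time limit

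*Combined protocol and SAP*

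**What the plan says.** Section 6.2.1 opens with the schedule: "Treatment with Ixazomib will use a cycle length of 28 days". The start of the following cycle is bounded: "The next cycle should begin as soon as possible, but no later than 14 days after the end of the previous cycle". An approval route follows at once: "Unavoidable deviations from this schedule will be permissible with prior approval by the Principal Investigator or Study Chair". To start a cycle the patient must meet neutrophil and platelet thresholds and a non-hematologic criterion: "All other non-hematologic toxicity (except for alopecia) must have resolved to" Grade 1 or lower, or to baseline.

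A patient who does not meet these criteria is put back a week and re-evaluated. The section then sets the end of the waiting: "The maximum delay before treatment should be discontinued will be 3 weeks or at the discretion of the Principal Investigator". Table 6-2 repeats this: "The maximum delay before treatment should be discontinued will be 3 weeks or at the discretion of the PI". That table is headed as dealing with hematologic toxicities, but the row holding this sentence also names non-hematologic toxicities above Grade 1.

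Table 6-3 deals with delays, reductions and discontinuations for non-hematologic events. For other Grade 3 toxicity related to study drug it says to hold, then branches at 4 weeks. If the patient has recovered by then, the action is "Reduce study drug 1 to next lower dose upon return to $<$ Grade 1 or baseline". In the other branch, "If not recovered to < Grade 1 or baseline within 4 weeks", the action is the same. A further row again takes Grade 3 toxicity unrecovered at 4 weeks and calls for the next lower dose, this time without waiting for recovery.

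Section 6.11 lists unresolved toxicity as a reason for discontinuation, gives no duration, and keeps such patients in follow-up for treatment failure.

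**The concern.** The passages cover the same patients. The restart criteria in 6.2.1 include non-hematologic toxicity, and so does the Table 6-2 row that carries the 3-week limit. A patient with related Grade 3 diarrhea who cannot start a cycle for more than 3 weeks therefore falls under both the 3-week rule and Table 6-3. One stops treatment unless the Principal Investigator decides otherwise. The other resumes treatment and does not tell the site to ask anyone.

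This is a multi-center trial, so different sites may follow different passages. Discontinuation for toxicity is not itself a treatment failure. Addition of a new systemic immune suppressive agent is (section 3.1), and a patient taken off ixazomib may be more likely to receive one. Inconsistent stopping could therefore affect the primary endpoint as well as exposure.

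**Working it through.** The plan gives no figure for how often or how long cycles are delayed, so there is none to reproduce. The check compares the passages and then counts days.

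**Passages side by side, for related Grade 3 non-hematologic toxicity**

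| Place | Limit | Apparent starting point | Consequence of exceeding it | Recovery needed |
|---|---|---|---|---|
| 6.2.1, scheduling sentence | 14 days | End of previous cycle | Prior approval needed; no discontinuation | Grade 1 or lower, or baseline |
| 6.2.1, delay sentence, and Table 6-2 | 3 weeks | Failed restart | Discontinue, or Principal Investigator discretion | Grade 1 or lower, or baseline |
| Table 6-3, two 4-week rows | None (branch at 4 weeks) | Start of hold | Resume one level lower in both branches | Below Grade 1, or baseline |
| Table 6-3, further row | None (applies at 4 weeks) | Start of hold | Next lower dose | None stated |

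The further row, read literally, lowers the dose of a patient whom the same table is still holding.

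**Day count.** Inputs: 28-day cycle, doses on Days 1, 8 and 15, limits of 14 and 21 days. The planned next Day 1 is day 28 + 1 = 29. Assumptions: delay is counted from that day, the 4 weeks run from the start of the hold, and a restart after day 29 begins the next cycle. For a hold that starts on day s and lasts h days:

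- restart day = s + h
- delay = s + h − 29
- delay exceeds 14 days when h > 43 − s
- delay exceeds 21 days when h > 50 − s

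| Hold starts | Past 14 days when h exceeds | Past 3 weeks when h exceeds |
|---|---|---|
| Day 8 | 43 − 8 = 35 | 50 − 8 = 42 |
| Day 15 | 43 − 15 = 28 | 50 − 15 = 35 |
| Day 22 (onset after the Day 15 dose) | 43 − 22 = 21 | 50 − 22 = 28 |
| Day 29 (next Day 1 missed) | 43 − 29 = 14 | 50 − 29 = 21 |

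Worked cases:

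- Day 29, 18-day hold: restart day 47, delay 18. Past the scheduling limit, inside the 3 weeks. Approval is needed; no passage stops the drug.
- Day 29, 25-day hold: restart day 54, delay 25. Stopped by default under 6.2.1; resumed under Table 6-3 as recovered within 4 weeks.
- Day 29, 35-day hold: restart day 64, delay 35. Stopped by default under 6.2.1; resumed under Table 6-3 as not recovered within 4 weeks.
- Day 8, 28-day hold: restart day 36, delay 7. No conflict.
- Day 15, 28-day hold: restart day 43, delay 14. No conflict.
- Day 15, 42-day hold: restart day 57, delay 28. Conflict.

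Table 6-3 has no ceiling, so every starting day has a hold length beyond which the two passages disagree. If the 3 weeks instead ran from the start of the hold, any hold longer than 21 days would be in conflict.

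**Recovery threshold.** A patient at Grade 1 whose baseline was lower may start a cycle under 6.2.1 but is still held under Table 6-3. That lengthens holds toward the disputed range. The sign should be checked against the signed protocol, because a lost underline would turn one threshold into the other.

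**The case against.** The best reply is that the passages have different jobs: 6.2.1 decides whether and when a cycle may start, and Table 6-3 gives the dose on return. A late return would then still need the Principal Investigator's decision, and only a cross-reference is missing. The layout gives this some support, since 6.2.1 sends the reader to the tables for dosing recommendations. But Table 6-3 says in its own title that it covers delays and discontinuations, and it does call for discontinuation elsewhere, for Grade 4 peripheral neuropathy. Its Grade 3 rows are silent on stopping and never point back to the 3 weeks. A site using the table alone has no reason to seek approval.

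Other parts of the reply stand, and they limit the point. A reader might infer:

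- **Three competing stopping rules.** The 14-day sentence has an approval route and never calls for discontinuation. For purely hematologic toxicity only the 14 days and the 3 weeks compete.
- **Mandatory discontinuation at 3 weeks.** The clause allows Principal Investigator discretion, so stopping is the default.
- **A conflict in every 4-week hold.** The day count shows that holds starting on Day 8 or Day 15 can last 4 weeks without breaching either limit.
- **A large cumulative delay, by applying the maximum at each of five cycle starts.** Table 6-2 and the Grade 3 rows of Table 6-3 cost a dose level each time. Table 6-1 has two reductions before discontinuation, and re-escalation is barred, so a third such delay generally ends treatment.
- **A number of patients at risk, from the Grade 3 or higher rates in Table 1-4.** Thrombocytopenia and neutropenia fall outside these Table 6-3 rows, and the rates do not show how many events stayed unresolved beyond 3 weeks.
- **A loss of power.** Section 7.1.1 uses 50 patients, failure rates of 44% and 29% (44 − 15), and a 1-sided alpha of 0.1. No delay rule enters, so the stated 82% is unaffected as a calculation. Any fall would need an assumed number of patients stopped and an assumed rise in their risk, and the documents give neither.

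**Conclusion.** The contradiction is real but narrow. It concerns related Grade 3 non-hematologic toxicity that blocks a new cycle for more than 3 weeks: ixazomib stops by default under 6.2.1 and Table 6-2, and resumes under Table 6-3. Within Table 6-3, the 4-week branch makes no difference to the action, and a further row reduces the dose with no recovery condition. Three secondary mismatches go with it: 14 days against 3 weeks, starting points that appear to differ, and below Grade 1 against Grade 1 or lower.

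Confidence is high on the text. The hold lengths at which the conflict begins (more than 21 to more than 42 days, by starting day) rest on the clock assumptions stated with the day count. The consequence is for who stays on drug and for consistency across sites. An effect on the 6-month failure rate is plausible but unquantified, because toxicity discontinuation is not a failure and follow-up continues after it. The passages should be reconciled; nothing here says which limit is right.

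**What to change.** Reconcile the passages by stating once, in 6.2.1:

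- one delay limit;
- the day from which it runs;
- whether exceeding it means discontinuation or a Principal Investigator decision;
- one recovery threshold.

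The 14-day sentence, the 3-week sentence, the Table 6-2 row and the 4-week rows of Table 6-3 should then all refer to that statement. The two identical branches of Table 6-3 should be merged or given distinct actions, and the further row should say whether recovery is required. The wording should also say whether the separate gap between cycles 6 and 7 in section 4.3 falls under the limit. The limit, the threshold and the consequence are for the sponsor-investigator to choose.

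Cost: amended wording in 6.2.1 and Tables 6-2 and 6-3, and a clarification to sites. No added procedures or patients and no change to the sample size.

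### Table 6-2 orders a one-level reduction after new painless Grade 2 neuropathy delays a cycle and resolves, where Table 6-3 orders the same dose

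*Combined protocol and SAP*

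**What the plan says.** Section 6.2.1 sets the conditions for starting a new cycle: an ANC threshold, a platelet threshold, and a non-hematologic condition that begins "All other non-hematologic toxicity (except for alopecia) must have resolved to" and continues with Grade 1 or less, or the patient's baseline. It then sends the reader to the tables: "For dosing recommendations for hematologic toxicities and non-hematologic toxicities, see Table 6-2 and Table 6-3 respectively".

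Table 6-2 is titled "Ixazomib Dose Adjustments for Hematologic Toxicities". Its row on subsequent cycles nevertheless lists, after low ANC and low platelets, "or other non-hematologic toxicities" above Grade 1 or not back to baseline. The action is to hold drug until the start criteria are met and then "Upon recovery, reduce Ixazomib 1 dose level".

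Table 6-3 is the non-hematologic table and has graded neuropathy rows. One reads "New or worsening Grade 1 peripheral neuropathy with pain or Grade 2". Grade 2 with pain has its own, stricter row, so the Grade 2 in this one is painless. The action is to hold until Grade 1 or less or baseline, then "Resume at same dose level".

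Table 6-1 gives the levels: 4.0 mg, 3.0 mg, 2.3 mg, then discontinue. The line closing Table 6-3 bars any return to a higher dose after a reduction.

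**The concern.** The two rows overlap on one event and give different doses for it. The non-hematologic clause in Table 6-2 is easy to apply in practice, because the row repeats the same three checks that Section 6.2.1 requires before drug is dispensed. Staff who have just delayed a cycle on those checks may well go to the row that mirrors them, and that row tells them to reduce.

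What is at stake is the dose of an individual patient whose neuropathy has already resolved. A reduction made this way is permanent under the protocol, and from the lowest level it means stopping the drug. In a multi-center trial, two sites could treat identical patients differently.

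**Working it through.** The plan states no figure on this point, so the check is a comparison of text followed by arithmetic on the dose levels.

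**Which patients meet both rows.**

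- Entered at Grade 0 or 1, with new painless Grade 2 neuropathy when a cycle is due: fails the cycle-start criterion, so both rows apply.
- Entered with painless Grade 2: Section 5.2, exclusion 10, allows this (it bars Grade 3 or above, and Grade 2 with pain). That state is the patient's baseline, the cycle-start criterion is met, and no cycle is delayed.
- Grade 1 with pain: in the same Table 6-3 row, but it does not exceed Grade 1 and so does not fail the cycle-start criterion.
- Grade 2 with pain, or Grade 3: both tables reduce by one level, so they agree.

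The conflict is therefore confined to new or worsening painless Grade 2 neuropathy that is still present when a cycle is due and then resolves within the permitted delay.

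**Side by side for that event.**

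| | Table 6-2, subsequent-cycle row | Table 6-3, neuropathy row |
|---|---|---|
| While active | Hold | Hold |
| After recovery | One level lower | Same level |

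**Size per affected patient.** Inputs: three doses per 28-day cycle (Section 6.1) and the levels in Table 6-1.

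| Level at the event | Table 6-3 dose, per cycle | Table 6-2 dose, per cycle | Difference per dose |
|---|---|---|---|
| 4.0 mg | 3 × 4.0 = 12 mg | 3 × 3.0 = 9 mg | 3.0/4.0 − 1 = −25.0% |
| 3.0 mg | 3 × 3.0 = 9 mg | 3 × 2.3 = 6.9 mg | 2.3/3.0 − 1 = −23.3% |
| 2.3 mg | 3 × 2.3 = 6.9 mg | 0 (discontinue) | drug stopped |

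For scale over the six planned cycles, assume no missed doses and no other reductions. The full course is 18 × 4.0 = 72 mg. The earliest cycle that can be delayed is the second, and a first-step reduction from there gives 3 × 4.0 + 15 × 3.0 = 57 mg, or 57/72 − 1 = −20.8%. A later event costs less; from cycle 6 it is 15 × 4.0 + 3 × 3.0 = 69 mg, or −4.2%.

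**How many patients.** This cannot be computed. Section 1.6 reports Grade 1 or 2 neuropathy in 6 of 52 patients in the weekly single-agent study. It does not separate painless Grade 2 or give timing, and the patients had a median of 2 cycles, so it does not bound a count over six.

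**The case against.** The strongest reply is that the protocol already settles the matter. The routing sentence sends non-hematologic toxicity to Table 6-3, both titles repeat the split, and a dedicated graded neuropathy row is more specific than a general clause in the other table. This largely stands. A reader might infer that the protocol gives no guidance on which table governs; the documents do not support that, and Table 6-3 is the probable intent. What the reply leaves is the clause itself. The table assigned to hematologic toxicity names non-hematologic toxicity in its own criteria, attaches a reduction to it, and no sentence explains or overrides it.

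A second reply is that harm needs a chain of events: a rise to painless Grade 2, persistence to the start of a cycle, recovery in time, and a site that acts on the wrong row. Section 6.2.1 is also headed as recommendations. This stands too, and it is why the point is minor.

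A reader might also infer a large loss of exposure by stacking reductions before the event. Nothing in the documents gives such a course any likelihood, so the per-dose steps are the fair measure.

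**Conclusion.** The inconsistency is real as written and minor. For one narrowly defined event, a row in Table 6-2 orders a reduction that Table 6-3 does not intend. The cost per affected patient is one permanent dose step, or the drug itself if the patient is already at the lowest level. The conclusion rests on reading the Table 6-3 row as covering painless Grade 2, which follows from the separate row for Grade 2 with pain.

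Three further inferences are not supported. Neither reading gives drug during an active event, since both tables hold until resolution, so this is not a case of dosing through toxicity. Sample size, power and the definition of 6-month treatment failure do not depend on it. And it does not show that Table 6-2 is, or should be, the rule for other non-hematologic events: for Grade 2 rash, for example, Table 6-3 leaves dose changes to discussion between the investigator and the project clinician.

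**What to change.** Keep the cycle-start hold and add one sentence to the subsequent-cycle row of Table 6-2: *For peripheral neuropathy, the dose on resumption follows Table 6-3.* Painless Grade 2 neuropathy that has resolved to Grade 1 or less, or to baseline, then resumes at the same dose level.

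The sentence should stop at neuropathy. Wording that made Table 6-2 the default for every event without a dose in Table 6-3 would confirm an irreversible reduction for Grade 2 rash that delays a cycle. It would do the same for events unrelated to the drug, because the Table 6-2 clause has no relatedness condition. Deleting the clause outright goes too far the other way: Table 6-3 gives no resumption dose for other Grade 2 events such as fatigue.

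The cost is a one-sentence edit and a memo to sites, with no new data or visits.

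### Table 6-3 gives the same action whether or not a related Grade 3 event recovers within 4 weeks, a later row drops the recovery condition, and neither is reconciled with the 3-week discontinuation limit in section 6.2.1 and Table 6-2

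*Combined protocol and SAP*

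**What the plan says.** All the text is in protocol section 6.2.1 and its tables.

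- **Cycle-start criteria.** Besides blood counts, a new cycle needs this: "All other non-hematologic toxicity (except for alopecia) must have resolved to" Grade 1 or lower, or to the patient's baseline.
- **Timing of the next cycle.** "The next cycle should begin as soon as possible, but no later than 14 days after the end of the previous cycle". The release clause follows: "Unavoidable deviations from this schedule will be permissible with prior approval by the Principal Investigator or Study Chair".
- **Limit on delay.** "The maximum delay before treatment should be discontinued will be 3 weeks or at the discretion of the Principal Investigator". Table 6-2 repeats this limit in a row on subsequent cycles. That row covers low counts "or other non-hematologic toxicities" above Grade 1, so the limit is not confined to hematologic events.
- **Table 6-3, other related Grade 3 non-hematologic toxicity.** The drug is held until the event falls below Grade 1 or to baseline. Two rows then cover recovery within 4 weeks and its opposite, "If not recovered to < Grade 1 or baseline within 4 weeks". Both prescribe the next lower dose upon return to that level. A recurrence row refers back to the guidance above it. A further row, "Grade 3 that does not recover to < Grade 1 or baseline within 4 weeks", says only to go to the next lower dose.

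**The concern.** A table that branches on recovery should do something different on each branch. Here two branches coincide, and a third entry for the same condition says something else. Read literally, the last row allows a reduced dose while the Grade 3 event is unresolved, although the same block says to hold and 6.2.1 says a cycle may not start.

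The second difficulty is stopping. Section 6.2.1 and Table 6-2 have a time-based route to discontinuation that expressly includes non-hematologic toxicity. The Table 6-3 Grade 3 rows have none, although the table's title includes discontinuations.

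This is a multi-center trial. Section 6.11 lists unresolved toxicity as a reason to stop drug and ties the End of Treatment visit to that stop. The last-dose date sets the 30-day adverse-event window in section 8.2. The discontinuation date enters the definition of treatment-related mortality in section 7.1.2. If sites follow different passages, these dates may reflect the site's reading as well as the patient's course.

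**Working it through.** The plan gives no figure here to reproduce. The check is a comparison of passages and a day count.

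**Step 1. The Grade 3 rows in Table 6-3.**

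| Row | Action | Recovery required first? |
|---|---|---|
| Initial | Hold | – |
| Recovered within 4 weeks | Down one level | Yes |
| Not recovered within 4 weeks | Down one level | Yes, eventually |
| Later row, Grade 3 not recovered within 4 weeks | Down one level | Not stated |

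Rows 2 and 3 are the same, so the 4-week test changes nothing. Rows 3 and 4 share a condition and differ on whether recovery must come first. Row 4 also conflicts with row 1 and with the cycle-start criteria.

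**Step 2. Stopping.** No row in this block stops treatment after a stated time. A patient already at the lowest dose in Table 6-1 would reach its discontinue level by one more reduction, but dose level drives that, not elapsed time. No text ranks Table 6-3 against 6.2.1 or Table 6-2.

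**Step 3. When 4 weeks meets the other limits.** Inputs: a 28-day cycle (6.2.1), dosing on days 1, 8 and 15 (6.1), and limits of 14 days and 3 weeks (6.2.1). Assumptions, because the protocol does not say: the 4 weeks start when the hold starts, the cycle calendar keeps running during a hold, and delay is counted from the next due date, day 29. For a hold beginning on cycle day d:

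- the 4-week window ends on day d + 28;
- the delay at that point is (d + 28) − 29 = d − 1 days;
- the hold that brings the delay to 21 days lasts 29 + 21 − d = 50 − d days.

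| Hold begins, day d | Window ends, day | Delay (days) | Over 14? | Over 21? | Hold length at 21-day delay |
|---|---|---|---|---|---|
| 1 | 29 | 0 | no | no | 49 |
| 8 | 36 | 7 | no | no | 42 |
| 15 | 43 | 14 | no | no | 35 |
| 16 | 44 | 15 | yes | no | 34 |
| 22 | 50 | 21 | yes | no | 28 |
| 23 | 51 | 22 | yes | yes | 27 |
| 29 (new cycle blocked) | 57 | 28 | yes | yes | 21 |

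Counting the 14 days from the end of day 28 instead moves that threshold from day 16 to day 15.

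The 4-week window therefore overruns the 3-week limit for holds from about day 23, or when a new cycle is blocked. For earlier holds it does not. But the non-recovery rows have no upper time limit, so a long enough hold from any day reaches 21 days of delay. There 6.2.1 points to discontinuation or discretion, and Table 6-3 to dose reduction.

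**Step 4. Primary endpoint.** Section 3.1 counts a new systemic immune-suppressive line, recurrent malignancy or death. Stopping ixazomib for toxicity is none of these, and follow-up continues after it (6.11). The definition does not depend on which passage a site follows.

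**The case against.** The strongest reply is that the clocks differ. The 4 weeks in Table 6-3 is a branch point that triggers no stop, while the 6.2.1 limits concern the start of a cycle. A reader might infer that anyone unresolved at 4 weeks should already have been discontinued. The documents do not support that: Step 3 shows that holds begun on a dosing day reach 4 weeks within the 3-week limit.

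Next, the limits are soft. The section is headed as recommendations, the 14-day rule yields to prior approval, and the 3-week rule yields to the Principal Investigator's discretion. The title page makes that person the sponsor-investigator, and section 8.3 refers separately to site principal investigators, so exceptions may be decided centrally. This weakens any claim that sites must diverge. It does not settle the matter: a site following Table 6-3 has no prompt to ask, and discretion over delay does not resolve the duplicated rows or the missing recovery condition.

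Third, the hold instruction and the cycle-start criteria still stand, so the last row need not be read as permission to dose through toxicity. That is a sensible reading, but the reader has to supply it. Confining the row to recurrences does not help, since the recurrence row already points back to the same guidance.

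Finally, a reader might see two conflicting recovery levels: below Grade 1 in this block, and Grade 1 or lower in 6.2.1 and the neuropathy rows. The symbol may have been altered when the text was read from PDF. Even if it is real, meeting the stricter level meets both. It needs checking and carries no weight here.

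**Conclusion.** The inconsistency is real and limited. The duplicated rows and the later row's missing recovery condition are plain on the text. The clash with the 3-week limit is conditional: it arises when toxicity blocks a cycle start, when the hold begins on about day 23 or later, or when the event stays unresolved long enough. The day thresholds rest on the counting assumptions stated with the table.

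The number of patients affected cannot be derived. A reader might take the 17% drug-related Grade 3 or higher diarrhea in study C16004 (Table 1-4) to mean about 0.17 × 50 = 8.5 patients. That figure is incidence, not failure to recover. It comes from a myeloma study with doses up to 3.95 mg/m² and expansion at 2.97 mg/m², which section 1.5 equates to about 5.5 mg, against a 4 mg start here. The documents give no rate of non-recovery at 4 weeks.

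The primary endpoint is unchanged by definition. The point deserves correction for patient safety and so that discontinuation and the dates that follow from it are handled alike across sites.

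**What to change.** The sponsor's clinical team should reconcile the Grade 3 rows of Table 6-3 with each other and with section 6.2.1 and Table 6-2. The amended text should state when each time limit starts, which passage governs where they meet, and whether the later non-recovery row is subject to recovery. The duplicated action and the recovery-grade symbol should be checked against the source document, because the table breaks across a page there. Which limit, recovery level or action is right is a clinical decision, and no view is taken on it. The cost is a wording amendment and notice to sites, with no added patients, procedures or data.
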